9.2 STATISTICAL METHODS

9.2.1 Adaptive Bayesian analyses

Clinical trial methodology needs to adapt to personalized medicine by including more frequent interim analyses of accumulating data, or by making greater use of those biomarkers information (Saad 2017; Janiaud 2019). An adaptive design is a clinical trial design that allows adaptations or modifications to aspects of the trial after its initiation without undermining the validity of the trial.

Therefore, the aim of the sequential analyses will be to detect treatment-by-biomarker interactions, that is, whether the treatment effect may be different according to biomarkers, that may potentially stop the recruitment of patients presenting with certain levels of that biomarker if there is any evidence that it interacts negatively with the outcome. Treatment effect will be assessed on two main outcome measures, namely a tolerance measure (to detect potential deleterious effects of treatment in some subsets) and an early surrogate efficacy measure (to detect a potential futility to continue treatment evaluation in some cohorts). As described above (section 4.8.2), the tolerance measure will be the occurrence within the first RECORDS" protocol, version 4.0 of 03/03/2021

7, 14 and 28 days of any grade 3 or over adverse events such as hospital-acquired infections, hyperglycemia, hypernatremia, neurological disorders, and the efficacy measure will be the number of vasopressor-free days within the first 28 days.

Search for treatment-by-cohort interactions will be based on each endpoint, and each cohort, separately. Let A and B denote the 2 treatment arms. The treatment effect, 0, of A over B will be considered as the parameter of interest.

Let consider a set of K biomarkers available at baseline, with $x_i = (x_{1i}, \dots, x_{Ki})$ the set of biomarkers for subject *i*, and $Y_{ii} = 1$ the outcome of subject i in arm j.

We will use a Bayesian inference. This is in line with the growing literature to propose Bayesian approaches in randomized clinical trial (), including to identify subpopulations with enhanced treatment effects (Simon 2018). Moreover, it allows to go further than the "statistically significant" findings based on p-values (Wasserstein 2019; Amrhein 2019). Last, Unlike in the frequentist evaluation of the influence condition, the Bayesian evaluation of the influence condition has the advantage of separating the parameters of clinical relevance and risk tolerance (Millen 2014), as detailed below.

Search for treatment-by-cohort interactions will be based on each biomarker and outcome, separately. Treatment-by-covariate interaction will be measured by a Bayesian criterion proposed by Millen (2014), based on the posterior probability of the 'interaction condition' defined in terms of the subpopulation effect sizes estimates:

$P(\hat{\theta}_+/\hat{\theta}_- \geq \lambda_1 | X) \geq \gamma_1,$

where X is the observed data, $\hat{\theta}_+$ is the treatment effect on the efficacy outcome in one subset and $\hat{\theta}_-$ in the remaining subpopulation, λ_1 is a threshold of clinically meaningful effect, close to that proposed by Morita (2014), and γ_1 represents the information threshold for decision-making. Inversely, it will apply to the tolerance outcome, based on

 $P(\hat{t}_+/\hat{t}_- \ge \lambda_2 | X) \ge \gamma_2$, where \hat{t}_+ is the treatment effect on adverse event in one subset and \hat{t}_- in the remaining subpopulation, λ_2 is a threshold of clinically deleterious effect, and γ_2 represents the information threshold for decisionmaking.

The estimates $\hat{\theta}_i$ or $\hat{\tau}_i$ will be defined according to the type of the endpoint, either continuous, with $\hat{\theta}_j$ = $\frac{\hat{\mu}_{Aj} - \hat{\mu}_{Bj}}{\hat{\sigma}_{i}}$, is the effect size defined within each subgroup as the mean treatment

difference divided by the common standard deviation, or binary $\hat{\tau}_j = \frac{\hat{p}_{Aj} - \hat{p}_{Bj}}{|\bar{p}_j(1 - \bar{p}_j)|}$ where \bar{p}_j is the estimated

average adverse event rate.

Noninformative prior distribution will be considered.

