4.1.2 Interventional phase

4.1.2.1 ELIGIBILITY CRITERIA (INTERVENTIONAL PHASE)

4.1.2.1 Inclusion Criteria (interventional phase)

- 1) Patients \geq 18 years old;
- 2) Admitted to the ICU with proven or suspected infection as the main diagnosis;
 - 3) Community acquired pneumonia related sepsis OR vasopressors dependency (norepinephrine, epinephrine, vasopressin, dopamine, phenylephrine) OR septic shock (Singer 2016: vasopressor to maintain mean blood pressure of at least 65 mmHg and lactate levels above 2 mmol/l) OR acute respiratory distress syndrome (ARDS Ranieri 2012: a- acute onset, i.e. within one week of an apparent clinical insult and with progression of respiratory syndrome, b-bilateral opacities on chest imaging not explained by other pulmonary pathologies, e.g. pleural effusion, atelectasis, nodules etc, c- no evidence for heart failure or volume overload, d-PaO2/FiO2 ≤ 300 mm Hg, PEEP ≥ 5 cm H2O

4) Patient who has signed an informed and written consent whevener he/she is able of consent, if not, if not ascent from his/her representant whenever he/she is present at time of screening for inclusion

- 5) Patients who have been tested for one or more RECORDS specific biomarkers
 - o CIRCI
 - o Endocan
 - o GILZ <
 - o CPD
 - o Transcriptomic SRS2
 - o Endotype B
 - o PCR COVD-19
 - o PCR Influenza
 - o PCR other respiratory virus

6) Affiliation to a social security system or to an universal health coverage (Couverture Maladie Universelle, CMU);

7) Patients under guardianship or curatorship will be included;

8) Patients in case of simple emergency (legal definition) will be included.

RECORDS" protocol, version 4.0 of 03/03/2021

16/61

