4.1.3.1 Biomarkers that are readilty available for bedside use for bedside use

1) *CIRCI "cohort"*: defined by baseline total cortisol of 10 μ g/dL or less OR a maximum increment in total cortisol of less than 9 μ g/dL at 30 and 60 minutes following a 250 μ g intravenous bolus of Synacthen (Annane et al). This biomarker is considered as the best available test for CIRCI, a syndrome of insufficient tissue activity of corticosteroids that may occur in critically ill patients like sepsis (Annane 2017a; Annane 2017b).

2) *Low plasma endocan cohort*: defined by levels of less than 2 ng/ml. This biomarker is an endothelial peptidoglycan that contribute regulating the inflammation by counteracting the leukodiapesis that is also a key target for corticosteroids (De Freitas Caires 2018; Gaudet 2017). Low circulating levels of endocan may result from insufficient release of exaggerated clearance. Then, low endocan levels may identify patients with a proinflammatory state (Gaudet 2018) that can be corrected by corticosteroids.

3) **CPD cohort**: defined by an increased circulating monocytes distribution width. Increased volume and other cell pathologic data (CPD) have been recently characterized as early index of sepsis and shown to correlate with severity and excesive systemic inflammation (Crouser 2017). This cellular biomarker has been approved by the FDA and can be very rapidly obtained as fast as the white blood cell count and on the same blood sample.

4) *Transcriptomic SRS cohort*: transcriptomic analysis of peripheral leukocytes defined two distinct sespsis response signatures SS1 and SRS2 (Davenport 2018). SRS1 is characterized by features of endotoxin tolerance, T -cell exhaustion, and downregulation of human leucocyte antigen (HLA) class II suggesting immune suppression whereas SRS2 may correspond to relative immune competency. Grouping septic patients relatively to SRS1 or SRS2 can reliably be done by using a generalized linear model based on the set of seven genes (DYRK2, CCNB1IP1, TDRD9, ZAP70, ARL14EP, MDC1, and ADGRE3). Previous work in rather small sized cohort of sepsis suggested increased mortality with hydrocortisone in SRS2 patients (Antcliffe 2018).

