4.5 Randomization Methods

4.5.1 Allocation sequence generation

[figure not shown]
A computer process will be used to generate allocation sequences in a 1:1. Any evidence suggesting increased harm in patients presenting with a contemplated biomarker will lead to the termination of recruitment of patients presenting with this biomarker and will qualify the corresponding biomarker for identifying patients who should not be treated by hydrocortisone plus fludrocortisone (see section 9). A randomization list will be generated beforehand by a computer program and verified according to the procedures of the sponsor, independently from the physicians who will recruit patients.

4.5.2 Stratification:

Randomization will be stratified on the following biomarkers:

- 1. CIRCI
- 2. Endocan
- 3. GILZ
- 4. CPD
- 5. Transcriptomic SRS2
- 6. Endotype B
- 7. COVID-19
- 8. Influenza
- 9. Other respiratory viruses

The full statistical analysis plan will be published before the first interim analyse.

According to the adaptive design of the umbrella trial, the number of biomarker strata is not fixed and will vary with 1) information gained from actual study participants on added-value of a specific biomarker, 2) from new biomarker released by RECORDS WP3-6, 3° from new relevant biomarker released in the literature that will be screened n a trimester basis throughout the study period. These novel biomarkers may include new clinical algorithm or phenotypes, new omic-derived signature, new biological biomarker issued from blood, urine or exhaled air.

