5.3 Baseline visit and randomisation visit

- Verification of inclusion and exclusion criteria
- patient demographics, source of infection, severity of illness (SAPS II and SOFA scores) (Le Gall 1993 Vincent), pre-existing comorbidities as defined in the Charlson comorbidity index (addendum 15.4.2) (Charlson 1994), Clinical Frailty Scale (addendum 15.43) (Rockwood 2005; Bagshaw 2014; Muscedere 2017).
- Core temperature, vital signs, central hemodynamic data (if available)
- Standard laboratory data including serum and urinary electrolytes, creatinine, urea, cholesterol ,triglycerides and glucose levels, arterial lactate levels, arterial oxygen tension and hemoglobin oxygen saturation, arterial pH, white blood cell counts, hemoglobin and hematocrit levels, INR, platelets count, total bilirubin levels.
- Microbiolology and virology, i.e. blood and any potential source of infection will be sampled for bacterial culture, nasopharyngeal, bronchial, or broncho-alveolar lavage fluid will be sampled for testing byPCR for SARS-CoV-2 and any other respiratory virus
- Synacthen test, i.e. blood sample for cortisol measurement immediately before and 30 and 60 minutes after 250µg intravenous bolus of corticotrophin.
- Whole blood samples will be collected for measurements of biomarkers described in WP3 and WP4. These blood samples will be managed within WP2.
- Interventions: mechanical ventilation, renal replacement, vasopressors, unblinded corticosteroids, thiamine, vitamin C, other vitamins, nutrition, intravenous fluids, blood products, anticoagulants, sedatives, stress ulcer prophylaxis, and antimicrobials),

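### Section 9.2.1 searches each marker's interaction separately, so a marker that merely travels with COVID-19 status or with a true effect modifier can be credited with an interaction it does not own

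*Protocol*

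**What the plan says.** Section 9.2.1 gives the rule twice: "Search for treatment-by-cohort interactions will be based on each endpoint, and each cohort, separately", and again "Search for treatment-by-cohort interactions will be based on each biomarker and outcome, separately". The criterion is the posterior probability that the standardised effect in one subset, divided by that in the rest of the population, passes a threshold. No other marker enters it.

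The same section gives each subject a vector of markers: "Let consider a set of K biomarkers available at baseline". Inclusion criterion 5 of the interventional phase reads "Patients who have been tested for one or more RECORDS specific biomarkers". The baseline visit (Section 5.3) lists "Synacthen test, i.e. blood sample for cortisol measurement immediately before and 30 and 60 minutes after" a corticotrophin bolus, together with viral PCR and the biomarker samples.

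Section 4.1.3.1 describes some markers in related terms. It says that "low endocan levels may identify patients with a proinflammatory state", and that increased monocyte volume and the other CPD measures are "shown to correlate with severity and excesive systemic inflammation". SRS1 and endotype A are both described as immune suppression. CIRCI (4.1.3.1) and GILZ (1.4.2) both index corticosteroid activity.

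Sections 4.1.3.1 and 5.11.4 set a different comparison for COVID-19 patients. They all receive dexamethasone and are randomised to fludrocortisone or its placebo only. All others are randomised to hydrocortisone plus fludrocortisone or placebos.

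Under Section 4.5.1, evidence of increased harm with a marker "will lead to the termination of recruitment of patients presenting with this biomarker" and qualifies that marker as identifying patients who should not be treated. Section 9.2.1 also allows recruitment at a marker level to stop on a negative interaction.

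**The concern.** When markers overlap, a one-at-a-time contrast picks up every other effect modifier whose frequency differs between marker-positive and marker-negative patients. The marker under test then shows an interaction that belongs to something else.

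COVID-19 is the clearest case, because it does not depend on an assumed biological correlation. The treatment contrast differs there by design. Read literally, 9.2.1 places COVID-19 patients in the subset or the remainder of every other marker's comparison. Any marker that is more or less frequent in COVID-19 then mixes two treatment comparisons in unequal proportions.

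The trial's main product is a list of markers that do or do not identify patients to treat. A wrong attribution shuts out bystander-positive patients who lack the true modifier. After a closure, carriers of the closed marker also stop entering the other cohorts, so the remaining contrasts average over a changed case mix.

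**Working it through.** **The plan's own figures (Section 9.1).** For a 3-day difference with SD 10, the normal approximation gives n = 2 × (1.96 + 0.842)² × 10² / 3² ≈ 175 per arm. With the stated 176 per arm, t-test power is 80.1%, against 80.04% stated, so the figure reproduces. The fourfold inflation for interactions gives 4 × 352 = 1,408. The maximum of 1,800 leaves 392/1,800 = 21.8% for dropout.

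**Assumptions (not in the protocol).** M is the only true modifier and X is a bystander with no role of its own. X has 50% prevalence. M is present in 60% of X-positive and 30% of X-negative patients, a correlation of 0.30. The effect is 3 days without M and 3 − d days with M. SD is 10, n = 1,408, allocation 1:1. The protocol gives no values for λ and γ, so one two-sided 5% test of the difference in effects stands in for the ratio criterion.

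**Size of the borrowed interaction.** Apparent interaction of X = −d × (0.60 − 0.30).

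| | d = 3 | d = 6 |
|---|---|---|
| Mean effect, X-positive: 3 − 0.6d | +1.2 days | −0.6 day |
| Mean effect, X-negative: 3 − 0.3d | +2.1 days | +1.2 days |
| Apparent interaction | −0.9 day | −1.8 days |
| SE, separate / joint | 1.072 / 1.120 | 1.088 / 1.120 |
| X flagged, separate (normal approximation) | 13% | 38% |
| X flagged, separate (simulation, 3,000 trials) | 13.3% | 37.4% |
| X flagged, joint model (simulation) | 5.1% | 5.4% |

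For d = 3, 0.9/1.072 = 0.84, and P(Z > 1.96 − 0.84) + P(Z < −1.96 − 0.84) ≈ 0.131 + 0.003 = 0.134. For d = 6, 1.8/1.088 = 1.65, and P(Z > 0.31) ≈ 0.38.

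The ratio scale is displaced too. With nearly equal SDs the ratio of effects for X is 1.2/2.1 = 0.57 (d = 3) or −0.6/1.2 = −0.5 (d = 6). It would be 1 if M and X were unrelated.

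**COVID-19.** The same formula applies, with M read as COVID-19 status and d as the difference between the two treatment contrasts. The protocol gives neither d nor the COVID-19 share by marker, so no figure can be put on it.

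**Sensitivity to correlation.** With n = 1,800, both prevalences 50%, a true interaction of −3 days and a posterior threshold of 0.975 (400 runs per setting), X is flagged separately in 2%, 12%, 36% and 58% of trials at correlations 0, 0.3, 0.5 and 0.7. The joint model flags it in 2–4%.

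**After closing M half-way (d = 6).** The second 704 entrants are all M-negative. The X-positive share among them is 0.20/(0.20 + 0.35) = 36%, or 256 patients. In total 608 are X-positive, 211 of them with M (34.7%), and 800 are X-negative, about 106 with M (13.2%). The apparent interaction is −6 × 0.215 = −1.3 days, and simulation flags X in 21%. Closure therefore shrinks the borrowed interaction here.

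**Cost of a joint model.** The SE rises by 1/√(1 − φ²): 1.05 at 0.3, 1.15 at 0.5 and 1.40 at 0.7. In the n = 1,800 setting, power for the true marker falls from about 0.88 to 0.75 at 0.5 and 0.61 at 0.7.

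**The case against.** - **The marginal contrast is a real average.** Section 9.1 aims to find patients who respond better, and X-positive patients do respond less well on average in the example. That stands. The error lies in crediting X and acting on it: the 40% of X-positive patients without M have the full 3-day benefit and would be shut out.
- **The percentages are not the protocol's error rates.** They come from one look and a difference test, with assumed inputs. With d = 3, X-positive patients still benefit by 1.2 days, so the 13% is not a rate of do-not-treat qualification under the harm wording of 4.5.1. It bears on the interaction wording of 9.2.1. This stands.
- **Overlap is implied, not stated.** Section 4.2 speaks of assigning a participant to a biomarker cohort, which could mean one cohort each. No rule is given for patients positive on several markers, and the vector notation and baseline testing point to overlap.
- **The SAP may add a joint model.** It may, but the separate search is fixed in the protocol itself.

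A reader might infer that all nine markers reflect two shared states. Three are viral PCR cohorts, so the text does not support that. A reader might also infer that interactions lose their meaning after a closure. Allocation stays 1:1 and stratified by marker, so the contrasts remain randomised; only the case mix changes.

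**Conclusion.** The point holds in a limited form. The protocol fixes a one-marker-at-a-time search, patients can carry several markers, and COVID-19 patients contribute a different treatment comparison. A marker can therefore show an interaction that belongs to COVID-19 status or to another marker, and be closed or qualified because of it.

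The illustrative size at correlation 0.3 is a borrowed interaction of 0.9 to 1.8 days, flagged in about 13% to 38% of trials against about 5% jointly. It is nil at correlation 0 and grows with the correlation. All of this rests on assumed prevalences, correlations and thresholds.

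It might seem to follow that no marker should be closed until it survives a full joint model. The documents and the arithmetic do not support that. The loss of precision can be large, up to nine markers may be only partly measured, and a truly harmful marker could be missed.

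**What to change.** In Section 9.2.1:

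1. Keep the separate search, and leave safety closures for harm free to act on it.
2. Before a marker is qualified, and for the final interaction estimate, also fit a model with treatment-by-COVID-19 and treatment-by-closed-marker terms, or analyse COVID-19 patients apart.
3. Report a joint model with the other measured markers as a supportive check, not as a mandatory gate.
4. After a closure, report the remaining markers within patients who do not carry the closed level.

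The cost is protocol or SAP wording, one more model and a stated rule for patients with unmeasured markers. The SE increase is about 5% at correlation 0.3 but about 15% at 0.5 and 40% at 0.7, which is why the full joint model should only support the decision.

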5.11.4 POSOLOGY AND DRUGS ADMINISTRATION

Initiation of treatments:

Treatment should be started immediately after randomization (day 0 of the study).

Posology:

- Hydrocortisone hemisuccinate /placebo will be given as 50 mg intravenous bolus every 6 hours

- Fludrocortisone /placebo* will be given as a 50 µg tablet via a nasogastric tube once per day in the morning

* Patients with COVID-19 will receive only experimental fludrocortisone or its placebo AND NOT hydrocortisone or its placebo as they will receive dexamethasone as the standard of care.

Duration of treatments:

Study drugs will be given until the patient will be discharge from the ICU for a maximal treatment duration of 7 days for steroids. Study drugs will be stopped without tapering off.

Reconstitution for IV injection of hydrocortisone/placebo:

Hydrocortisone hemisuccinate lyophilisate will be reconstituted prior to use with 2 mL water for injection. The solvent must be injected gently into the vial. Reconstitution and dilution should be performed in accordance with Good Clinical Practices guidelines, particularly with respect to asepsis and to Hydrocortisone SmPC. Hydrocortisone must not be used if the reconstituted solution has a cloudy appearance or contains floccular or particulate matter. The SmPC instructions for use, handling and disposal should be strictly followed.

The volume injected will be 1 mL, containing 50 mg of Hydrocortisone.

"Administration of fludrocortisone/placebo

A 50 μ g fludrocortisone/Placebo tablet is administered, enterally, once a day. For patients with a nasogastric tube, the entire tablet will be introduced into the nozzle of the tube. The tube will be flushed with 50 mL of water (the 10 first mL have to be injected slowly) and clamped for at least 30 minutes after tablet administration."

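### The tolerance criterion in 9.2.1 is a ratio with no sign condition, so it gives the same value for a steroid excess and a mirrored placebo excess of adverse events

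*Protocol*

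**What the plan says.** Section 9.2.1 (Adaptive Bayesian analyses) introduces the arms with "Let A and B denote the 2 treatment arms" and takes the effect of A over B as the parameter of interest. It does not say which arm is active. An efficacy criterion is given first, as a ratio of the effect in one subset to the effect in the rest. The tolerance criterion follows: "Inversely, it will apply to the tolerance outcome, based on" P(t+/t- ≥ λ2 | X) ≥ γ2. Here t+ "is the treatment effect on adverse event in one subset and" t- is its counterpart in the remaining subpopulation. For a binary endpoint, t is (pA − pB) divided by |p̄(1 − p̄)|. Despite the opening word, the ratio and the direction of the inequality are those of the efficacy criterion. No condition is placed on the sign of t+ or t-.

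The surrounding text does have a direction. In 9.2.1 the tolerance measure exists "to detect potential deleterious effects of treatment in some subsets", recruitment for a biomarker may stop "if there is any evidence that it interacts negatively with the outcome", and λ2 is itself described as marking a deleterious effect. Section 4.5.1 states the consequence: "Any evidence suggesting increased harm in patients presenting with a contemplated biomarker will lead to the termination of recruitment", and the finding "will qualify the corresponding biomarker for identifying patients who should not be treated by hydrocortisone plus fludrocortisone".

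**The concern.** The words ask whether steroids cause more adverse events in the cohort than elsewhere. The formula asks only whether the cohort effect is at least λ2 times the effect elsewhere, in whichever direction both effects point. A ratio of two negative numbers is positive, so a cohort in which placebo patients have the larger excess can meet the written criterion.

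This is the stated decision quantity for the safety adaptation. Section 4.5.1 links a harm finding to ending recruitment of the cohort and to labelling its patients as unsuitable for the treatment. The data analyst is blinded under 4.6. An analyst working with coded arms would get the same answer under either coding, so the output alone would not say which arm has the excess.

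**Working it through.** The plan gives no figure for this rule, so there is none to reproduce. The first step needs no assumed numbers.

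**1. Algebra.** The denominator |p̄(1 − p̄)| is positive, so t has the sign of pA − pB. Reversing both effects gives (−t+)/(−t-) = t+/t-. Exchanging the labels A and B does exactly this. Naming the arms therefore changes nothing by itself; the cause is the missing sign condition.

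**2. Worked example (rates assumed).**
- Steroid excess, A = steroid: 40% v 20% in the cohort, 35% v 25% in the rest. In both subsets p̄ = 0.30 and p̄(1 − p̄) = 0.21. So t+ = 0.20/0.21 = 0.952, t- = 0.10/0.21 = 0.476, and the ratio is 2.00.
- Mirrored placebo excess: t+ = −0.952, t- = −0.476, and the ratio is again 2.00.
- Only the rest reversed (40% v 20%; 25% v 35%): the ratio is −2.00. The equality therefore needs both subsets to reverse together.

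**3. Posterior probabilities for the example.** Beta(1,1) priors (the protocol says only that the prior is noninformative), 200 patients per arm per subset, 400,000 draws:

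| λ2 | Steroid excess | Placebo excess | Placebo excess, t+ > 0 required |
|---|---|---|---|
| 1 | 0.927 | 0.928 | 0.000 |
| 1.25 | 0.836 | 0.836 | 0.000 |
| 1.5 | 0.716 | 0.714 | 0.000 |
| 2 | 0.485 | 0.485 | 0.000 |

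Requiring t+ > 0 leaves the steroid-excess column unchanged. With only the rest reversed, the probability is about 0.015.

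**4. How often the rule would fire at an interim look.** Assumed: 45% v 30% in the cohort, 35% v 30% in the rest, cohort 180 and rest 720 (900 patients, half the 1800 maximum), 1:1 arms, Beta(1,1) priors, λ2 1.5, γ2 0.8.

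| Run | Steroid excess, as written | Placebo excess, as written | Placebo excess, t+ > 0 required |
|---|---|---|---|
| 4,000 looks | 15.7% | 14.9% | 0% |
| 1,500 looks | 16.0% | 16.9% | 0% |

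Differences between the two directions are Monte Carlo error. Firing under steroid excess is unchanged by the sign condition.

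Sensitivity (4,000 looks, placebo excess, rule as written):
- λ2 1.5 with γ2 0.7 / 0.8 / 0.9: 30 / 15 / 4%.
- γ2 0.8 with λ2 1.25 / 1.5 / 2: 21.8 / 14.9 / 5.8%.

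With 30% in every arm, the rule as written fires in 0.12% of looks (λ2 1.5, γ2 0.8).

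**5. What the sign condition does not change.** With t+ > 0 and λ2 positive, the criterion also needs t- > 0. If the rest has no effect, about half the posterior lies on the wrong side of zero: for 40% v 20% against 30% v 30% the probability is 0.493 at λ2 1.5. In the step 4 setting, with 45% v 30% in the cohort, the rule fires in 4.1% of looks when the rest is null and in 0.2% when the rest is protected. These figures are the same with and without the sign condition.

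**The case against.** The strongest reply is that the intended direction is not in doubt. It is stated in 4.5.1, in the purpose given in 9.2.1, and in the description of λ2 beside the formula. The formula is presented as a measure of interaction, and the action follows from the wording. Under 7.3.4 the DSMB advises and the sponsor decides, and 4.5.2 promises a full statistical analysis plan before the first interim analysis. All of this stands. A reader might infer that the trial would close a cohort because steroids reduced adverse events. The documents do not support that: such a closure would contradict every statement of purpose, and nothing makes the formula act automatically.

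What does not stand is that the matter is only left open. Values of λ2 and γ2 may properly wait for the analysis plan and are not counted as missing. The form of the criterion, however, is written in full here, and it disagrees with the words it serves.

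Two further limits are fair. Section 5.14.2 lists these events as associated with corticosteroids, so a placebo excess in both subsets, relatively larger in the cohort, is not the expected pattern. And higher firing rates, such as the 41.8% found for a cohort of 360 with 1440 in the rest, belong to settings that total 1800 patients. Recruitment is then complete and no cohort is left to close, so those settings illustrate the algebra only.

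**Conclusion.** The criterion is wrong as written: when both subset effects reverse together, it cannot tell harm from steroids from the mirrored excess on placebo. That follows from algebra alone. The size, about 15 to 17% of looks in either direction with 900 patients enrolled, rests on assumed rates, thresholds and priors; over the values tried in that setting it runs from 4% to 30%.

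Two stronger readings should be resisted. A reader might blame the unnamed arms, but naming them leaves the ratio as it is and matters only once a sign is required. A reader might also take the formula to be blind to direction in every case, but if only one subset reverses the ratio turns negative and the signal almost vanishes. Because the intended direction is clear and the triggering pattern unlikely, priority is low to moderate. It is still worth correcting before the first interim analysis.

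**What to change.** In 9.2.1, add text to this effect:

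*A is the active arm (hydrocortisone plus fludrocortisone; fludrocortisone in the COVID-19 cohort) and B is placebo. The tolerance signal is P(t+ > 0 and t+/t- ≥ λ2 | X) ≥ γ2. It is one trigger and does not limit closure on other evidence of harm under 4.5.1.*

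The COVID-19 wording is needed because section 5.11.4 says "Patients with COVID-19 will receive only experimental fludrocortisone or its placebo AND NOT hydrocortisone" or its placebo. The text should not say that a cohort closes only if the signal is met. That would make the ratio a necessary condition, contradict 4.5.1, and block closure in the cases where the ratio rarely fires.

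The cost is two or three sentences, with no new data. The blinded analyst can compute the signal under both codings. Someone holding the allocation must then say which coding applies, but acting on increased harm under 4.5.1 already requires that. In the setting shown, the sign condition loses no firing under steroid excess.

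The change corrects direction only. Detecting harm in a cohort when the rest is null or protected would need a different form of criterion, with its false-closure rate calibrated by simulation first.
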